## Table 5: Safety Reporting

Reconciliation of SAEs (reported to Sponsor as per SOP) will be carried out by the TCTU Data Management Team; the Sponsor representative will provide the reported SAEs to TCTU.

All AEs will be MedDRA (26) coded by the TCTU Data Management Team.

## 10.1.1 AE & SAE Exception List

Due to the large amount of comorbid disease and very high levels of illness and adverse events that we expect to be present in this population, we will record all Adverse Events but not report to REC those classified as SAEs, in the following categories:

- Any death or hospitalisation due to a new cardiovascular event
- Any death or hospitalisation due to new diagnosis or treatment of cancer

- Any death or hospitalisation due to exacerbation of an existing medical condition
- Any admission for elective or planned investigation or treatment
- Any death or hospitalisation due to nausea, vomiting, constipation or diarrhoea
- Any death or hospitalisation due to a fall.

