#### **10 SAFETY ASSESSMENTS**

As the study is defined as a non-Clinical Trial of Investigational Medicinal Product, Adverse Events (AE) and Serious Adverse Events (SAE) not defined on the exception list (see Section 10.1.1) will be recorded and reported as per Health Heath Research Authority (HRA) and Sponsor's guidelines for non-CTIMP reporting (summarised in Table 5**Error! Reference source not found.**).

A serious adverse event (SAE) is defined as an untoward occurrence that:

- (a) results in death;
- (b) is life-threatening;
- (c) requires hospitalisation or prolongation of existing hospitalisation;
- (d) results in persistent or significant disability or incapacity;
- (e) consists of a congenital anomaly or birth defect; or
- (f) is otherwise considered medically significant by the investigator.

Note: Hospitalisations for treatment planned prior to randomisation and hospitalisation for elective treatment of a pre-existing condition will not be considered as an SAE. However, any adverse events occurring during such hospitalisation will be recorded. See section 10.1.1 for further AE and SAE reporting exemptions.

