#### 10.1 RECORDING AND REPORTING AEs AND SAEs

AEs and SAEs will be recorded from the time of written informed consent until the last study visit.

- Only AEs which have resulted in the participant seeking advice or treatment from a healthcare professional will be recorded.
- The PI or delegate will ask about the occurrence of AEs and hospitalisations visits 2 and 4 only.
- Once the Investigator becomes aware that an AE or SAE has occurred in a study participant, they
  must enter the information into the CRF AE Log and entered (in a timely fashion) into the
  OpenClinica database.

• Participants with unresolved AEs at the last study visit will be followed up until resolution or 30 days after their last study visit, whichever is sooner.

An SAE occurring to a research participant will only be reported as per HRA guidelines to the main REC, and copied to the Sponsor (as per University of Aberdeen SOP) via [contact], where in the opinion of the Chief Investigator the event was:

Related - that is, it resulted from administration of any of the research procedures, and

*Unexpected* – that is, the type of event is not listed in the protocol or Reference Safety Information (section 6.3) as an expected occurrence.

unless meeting a AE/SAE reporting exception category, as outlined in section 10.1.1 (below).

	Who	When	How	To whom
SAE	Chief Investigator (CI)	Within 15 days of the	SAE report form for non-	Main REC for the
		CI becoming aware of	CTIMPs	study.
		the event		
Urgent safety	Chief Investigator (CI)	(i) Immediately	(i) By telephone	Main REC: study
measures	or sponsor	(ii) Within 3 days	(ii) Notice in writing setting	co-ordinator will
	Or exceptionally by		out the reasons for urgent	acknowledge
	local principal		safety measures and the	within 30 days
	investigator (PI)		plan for further action	

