## 12.3 DATA MONITORING

An independent data monitor, [name] (Senior Clinical Lecturer) will review the study protocol and CRF prior to study commencement and report on final study data, provided by the study statistician, at the end of the study; and if/as requested by the study funder. In addition the Statistical and Health Economic Analysis Plans will be reviewed by the independent data monitor. A charter containing details of role, reporting and accountability for the independent data monitor will be produced prior to the commencement of the study.

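### Because 10.1 already limits REC reports to related, unexpected SAEs, the 10.1.1 exception list, read literally, only withholds 15-day reports of events the CI attributes to the trial

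*Protocol*

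**What the plan says.** Section 10.1 sets the base rule: "An SAE occurring to a research participant will only be reported as per HRA guidelines to the main REC", copied to the Sponsor, where the Chief Investigator holds that two conditions are met. The event must be related, worded as "it resulted from administration of any of the research procedures, and" it must be unexpected, meaning that "the type of event is not listed in the protocol or Reference Safety Information (section 6.3) as an expected occurrence". A third condition follows: "unless meeting a AE/SAE reporting exception category, as outlined in section 10.1.1 (below". Table 5 and section 10.2 set 15 days for the report.

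Section 10.1.1 explains the list by the heavy comorbidity and high event rate expected in this population, and states its effect: "we will record all Adverse Events but not report to REC those classified as SAEs, in the following categories". Six categories follow: new cardiovascular events, cancer, "Any death or hospitalisation due to exacerbation of an existing medical condition", elective or planned admissions, gastrointestinal symptoms, and falls. None is limited to events judged unrelated.

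The opening sentence of section 10 says that AEs and SAEs "not defined on the exception list (see Section 10.1.1) will be recorded and reported" under HRA and Sponsor guidelines. Section 10.3 promises the REC a yearly safety form giving causally related SAEs, and mentions no exception list. Section 10.4 provides for urgent safety measures, with written notice to the REC and Sponsor within three days. Under section 12.3 the independent data monitor is to "report on final study data, provided by the study statistician, at the end of the study", or at the funder's request.

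**The concern.** The reason given for the list does not match what it does. Admissions and deaths from pre-existing illness, unconnected with the trial, are excluded from REC reporting by the relatedness test before the list is consulted. What remains for the list to remove is an event that the Chief Investigator has attributed to the trial and did not expect.

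The categories matter in this trial. Every participant has iron deficiency anaemia and one arm stops oral iron. An admission for worsening anaemia fits the exacerbation category on its words, and section 1.1 itself associates anaemia with increased hospitalisation and mortality. At stake is the speed at which the REC, and through the copy the Sponsor, learns of a death or admission believed to be caused by the trial. Capture of the data and the feasibility co-primary outcomes are not affected.

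**Working it through.** No sample size, error rate or other figure is involved, so the check is one of logic. The inputs are the three conditions in section 10.1 and the list in 10.1.1. Write R for judged related, U for unexpected, and E for falling in a listed category.

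- Rule without the list: report if R and U.
- Rule as written: report if R and U and not E.

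| R | U | E | Without list | As written |
|---|---|---|---|---|
| yes | yes | yes | report | **no report** |
| yes | yes | no | report | report |
| yes | no | yes | no report | no report |
| yes | no | no | no report | no report |
| no | yes | yes | no report | no report |
| no | yes | no | no report | no report |
| no | no | yes | no report | no report |
| no | no | no | no report | no report |

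Reportable combinations fall from 2 of 8 to 1 of 8. The only row that changes is the related, unexpected, listed event. The two rows with R = no and E = yes hold the background illness that the list was written for, and they give no report under either rule. The list therefore saves no reports of unrelated events.

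**Second reading.** Section 10.1 defines unexpected by reference to what is listed in the protocol or in the Reference Safety Information, so 10.1.1 could be taken as the protocol's list of expected events. Let S mean listed in the Reference Safety Information.

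- Reading A (list as a separate exemption): U = not S, so report if R and not S and not E.
- Reading B (list as expected events): U = not S and not E, so report if R and not S and not E.

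The same events are withheld under both. Only the step that removes them differs.

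**Which categories have practical effect.**

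| Category | Already removed elsewhere? |
|---|---|
| New cardiovascular event | Not by any other stated rule if judged related and unexpected |
| Cancer | Same |
| Exacerbation of an existing condition | Same; can include worsening anaemia |
| Fall | Same |
| Elective or planned admission | Mostly: section 10 keeps most of these outside the SAE definition |
| Nausea, vomiting, constipation, diarrhoea | Probably: section 1.1 describes gastrointestinal side effects of oral iron in up to 40% of people, and SmPC section 4.8 is the reference safety information (7.2) |

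That leaves 6 − 2 = 4 categories carrying most of the effect.

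**Stopping iron.** Section 10.1 ties relatedness to the administration of a research procedure. If withdrawing a drug is not administration, harm from stopping iron fails R and never reaches the list. If it is, a listed event is removed by the list. Either way there is no 15-day report, so correcting the list alone would not settle this case.

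**Other routes.** Recording continues under 10.1 and 10.1.1. The annual form in 10.3 can carry related SAEs, but up to 12 months after the event against 15 days. The route in 10.4 operates only if an urgent measure is taken.

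**The case against.** The strongest reply is that this is a small non-CTIMP of treatments in ordinary NHS use, that all events are recorded, and that the REC has two other routes: the annual report of causally related SAEs, and notice within three days of any urgent safety measure. That stands, and it limits the severity. It does not close the gap, because the annual form can be months late and an urgent measure depends on someone deciding to take one. The annual form also sits awkwardly with the statement in 10.1.1 that these SAEs are not reported to the REC.

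A second reply is that 10.1.1 may be meant as the list of expected events. That is possible, but the working shows that the same events go unreported.

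A third is that an existing medical condition means comorbidity rather than the anaemia under study. The stated rationale supports this, but the category does not say so. A site could read it either way.

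A reader might infer more than the protocol supports:

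- *A trial-caused death could never reach the REC.* Sections 10.3 and 10.4 leave routes open.
- *The Sponsor would certainly not be told.* The exemption in 10.1 appears to cover the Sponsor copy, but 10.1.1 mentions only the REC, and the Sponsor's SOPs are not shown.
- *All six categories are equally affected.* The elective and gastrointestinal categories largely drop out on other grounds, though the SmPCs are not available to confirm the second.
- *Harm from stopping iron is hidden by the list.* It may already fail the relatedness wording.
- *Listed events go unrecorded.* The opening sentence of section 10 implies this, but 10.1 and 10.1.1 expressly require recording, so it is a drafting conflict.

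**Conclusion.** The concern holds as a defect in expedited reporting. Read literally, the list changes exactly one of eight combinations: it withholds the 15-day report of SAEs judged related and unexpected, mainly in four categories. Its stated purpose is already met by the relatedness test. This conclusion does not depend on whether the list is read as an exemption or as expected events.

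How many events would be affected cannot be estimated, because the protocol gives no SAE rates. Among 84 participants it is probably few. The conclusion assumes that no Sponsor SOP outside the protocol overrides the list. Severity: should fix. It concerns prompt safety oversight, not data capture or the trial's main results.

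**What to change.** 1. Add to 10.1.1: *These exceptions do not apply to, and do not make expected, any SAE judged related to a trial strategy. Such SAEs, if not listed in the Reference Safety Information, are reported within 15 days as in Table 5.*
2. State in 10.1 that related includes events resulting from the allocated strategy (continuing, stopping or switching iron), not only from administration of a procedure.
3. Reword the opening sentence of section 10 so that listed events are clearly recorded, in agreement with 10.1.1, and make 10.1.1 consistent with the annual report in 10.3.

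Deleting the exemption clause from 10.1 would not be enough, because 10.1.1 itself says that these SAEs are not reported to the REC. The changes are to protocol wording only and alter no treatment rule. The cost is an amendment and possibly a few extra expedited reports. Unrelated background events would stay unreported, as intended.

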## **10.2 REGULATORY REPORTING REQUIREMENTS**

The CI will inform Sponsor & REC within 15 days of any reportable SAE or Urgent Safety Measure; as per HRA guidelines for Non-CTIMP safety reporting (summarised in Table 5**Error! Reference source not found.**).

## **10.3 ANNUAL REPORTING REQUIREMENTS**

The following reports will be submitted each year as a condition of the authorisation to undertake a clinical trial or as a condition of a favourable opinion from a REC:

- NRES Annual Progress Report will be prepared and submitted by the CI to REC, and copied to Sponsor, on the anniversary date of the REC favourable opinion.
- NRES Safety Report Form will be sent to the REC. This will provide details of causally related SAEs (occurring in the UK), Urgent Safety Measures and any other safety reports submitted (for example: Data Monitoring Committee reports).
- These reports will be copied to the Sponsor.

## 10.4 URGENT SAFETY MEASURES

The CI or other clinician may take appropriate immediate urgent safety measures in order to protect the participants of the study against any immediate hazard to their health or safety. The REC and Sponsor will be notified in writing within three days.

## 11 PREGNANCY

The target population are of an age to preclude pregnancy

## 12 STUDY MANAGEMENT AND OVERSIGHT ARRANGEMENTS

## 12.1 TRIAL MANAGEMENT GROUP (TMG)

The study will be coordinated by a Trial Management Group, consisting of Chief Investigator, Principal Investigators, and key grant holders, study co-ordinator and relevant TCTU staff.

## 12.2 TRIAL MANAGEMENT/COORDINATION

A Study Coordinator will be based at the Sponsor site, and will liaise closely with the TCTU Trial Manager. The Trial Manager will form the central point of coordination for the study, with oversight and guidance given by a senior staff member at TCTU; all three will be accountable to the Chief Investigator.

A Delegation Log will be prepared for each site, detailing the role of each member of staff working on the study. The PI is responsible for maintaining the Delegation Log. Copies of the Delegation Log, study specific training records (Site Initiation Training attendance record, SOP reading log, Operations Manual confirmation of reading, electronic systems certificates of training), signed Curriculum Vitae and Good Clinical Practice certificates (including updates) will be provided to the Trial Manager / delegate for review to ensure that all staff are appropriately qualified and trained for their delegated role. Regular communication, including teleconferences, will ensure that site staff share best practice. Refresher training will be provided by the trial manager where no study activity has been undertaken for a period of 3 months or more.

## 12.3 DATA MONITORING

An independent data monitor, [name] (Senior Clinical Lecturer) will review the study protocol and CRF prior to study commencement and report on final study data, provided by the study statistician, at the end of the study; and if/as requested by the study funder. In addition the Statistical and Health Economic Analysis Plans will be reviewed by the independent data monitor. A charter containing details of role, reporting and accountability for the independent data monitor will be produced prior to the commencement of the study.

## 12.4 INSPECTION OF RECORDS

The CI, PIs and all institutions involved in the study will permit study related monitoring, audits, REC review, and regulatory inspection(s). In the event of an audit, the CI will allow the Sponsor, representatives of the Sponsor or regulatory authorities direct access to all study records and source documentation.

#### 12.5 RISK ASSESSMENT

A study risk assessment was carried out by the Research Governance Manager of the Sponsor prior to Sponsorship approval being granted.

#### **12.6 STUDY MONITORING**

The Sponsor will determine the appropriate extent and nature of monitoring for the study and will appoint appropriately qualified and trained monitors if required. Any monitoring will be provided within the Monitoring Plan. For monitoring purposes the Source Data Identification list, generated by the Trial Manager / delegate and secure, password protected access to TRuST, OC and Excel spreadsheets will be provided.

#### 12.6.1 Potential Risks

• Risks associated with invitation to participate:

Potential participants may not be aware that their oral iron supplementation has not improved their anaemia. To avoid causing concern, and any potential adverse impact for the GP-Patient relationship, text relating to suboptimal response has been avoided in the participant information and invitation letters.

• Risks associated with study outcome procedures:

Venepuncture carries the risk of bruising and discomfort, but will be undertaken by experienced staff with access to additional staff if required.

Study visits potentially can lead to fatigue due to travel and attendance. All participants will have access to taxi transport and will be given time to rest between each study assessment. Participants will be able to rest after each visit, and will be offered refreshments.

Close monitoring of patients in the study has the potential to uncover new diagnoses or clinically important findings. The PI will communicate to the participant's GP, in writing, any relevant incidental findings with participant's consent.

• Risks associated with medication used in treatment strategies:

These include known side effects of oral and IV iron, drug hypersensitivity reaction, and idiosyncratic reaction. All sites which will deliver the IV iron medication have facilities to deal with any acute reactions including to severe anaphylaxis and cardio-respiratory arrest situation. Any signs or

indications of potential side effects during IV therapy will be monitored closely by the Nurse who will be present with the participant throughout the IV administration.

## 12.6.2 Minimising Risk

All associated risks for both oral and intravenous iron use are well understood and have established procedures for management as part of their use in routine NHS care where the treatments will be delivered.

Participants will receive contact and emergency contact details in PIS and via a Participant Study Card. These study staff contact details will enable patients to contact staff with any concerns and to allow the study team to support participants in the event of any adverse event that cannot be dealt with via usual NHS services.

All patients will have access to taxi transport for each visit to aid accessibility, convenience and retention. Travel costs will be reimbursed.

Risks of venepuncture will be discussed and undertaken by experienced staff with access to additional staff if required.

The screening process will reduce risk by excluding those people where study procedures/intervention would interfere with current best medical practice in managing any comorbid disease.

## 13 GOOD CLINICAL PRACTICE

## 13.1 ETHICAL CONDUCT OF THE STUDY

The study will be conducted in accordance with the principles of good clinical practice (GCP) and the UK Policy Framework for Health and Social Research (22). In addition to Sponsorship approval, a favorable ethical opinion will be obtained from an appropriate REC and appropriate NHS R&D permissions will be obtained prior to commencement of the study.

## 13.1.1 Confidentiality

All laboratory specimens, evaluation forms, reports, and other records will be identified in a manner designed to maintain participant confidentiality. All records will be kept in a secure storage area with limited access to study staff only. Clinical information will not be released without the written

permission of the participant, except as necessary for monitoring and auditing by the Sponsor, its designee or Regulatory Authorities.

The CI and study staff involved with this study will not disclose or use for any purpose other than performance of the study, any data, record, or other unpublished, confidential information disclosed to those individuals for the purpose of the study. Prior written agreement from the Sponsor or its designee will be obtained for the disclosure of any said confidential information to other parties.

## 13.1.2 Data Protection

The CI and study staff involved with this study will comply with the requirements of the Data Protection Act 1998 and subsequent update to General Data Protection Regulations, with regard to the collection, storage, processing and disclosure of personal information and will uphold the Act's core principles. The CI and study staff will also adhere, if appropriate, to the current version of the NHS Scotland & England Code of Practice on Protecting Patient Confidentiality. Access to collated participant data will be restricted to the CI and appropriate study staff.

Computers used to collate the data will have limited access measures via user names and passwords.

Published results will not contain any personal data that could allow identification of individual participants.

## 13.1.2 Insurance and Indemnity

The University of Aberdeen and NHS Grampian are Co-Sponsoring the study.

Insurance: select the applicable text form the list below:

- University of Aberdeen will obtain and hold a policy of Public Liability Insurance for legal liabilities arising from the study.
- Grampian Health Board will maintain its membership of the Clinical Negligence and Other Risks Insurance Scheme ("CNORIS") which covers the legal liability of Grampian in relation to the study.
- Where the study involves University of Aberdeen staff undertaking clinical research on NHS patients, such staff will hold honorary contracts with Grampian Health Board which means they will have cover under Grampian's membership of the CNORIS scheme.

**Indemnity:** The Co-Sponsors do not provide study participants with indemnity in relation to participation in the Study but have insurance for legal liability as described above.

## 14 STUDY CONDUCT RESPONSIBILITIES

## 14.1 PROTOCOL AMENDMENTS

The CI will seek Sponsor approval for any amendments to the Protocol or other study documents. Amendments to the protocol or other study docs will not be implemented without approval from the Sponsor and subsequent approval of substantial amendments from the appropriate REC and NHS R&D Offices.

